6.3.5. Healthcare costs and utilization

A combination of administrative data, survey data, and microcosting approaches are used to estimate costs over the 6 months after randomization. Utilization of healthcare services, including laboratory tests, office visits, time demands, transportation cost, and hospitalization information will be derived from both end-of-study participant surveys and CDW administrative data.^{23,24} Estimates of the infrastructure and personnel needed to deliver the intervention are derived empirically from the study. Healthcare costs are abstracted from billing and administrative data from the CDW and CMS data.

6.4 Other exploratory outcomes

6.4.1. Self-reported patient activation

Self-reported understanding, competence, and willingness to participate in health care decisions and processes are assessed via the baseline and end-of-study surveys, using the 13-item short form of the Patient Activation Measure (PAM-13).¹³ Each PAM-13 item has four possible response options: “Strongly disagree” (1), “Disagree” (2), “Agree” (3), “Strongly agree” (4), as well as “Does not apply” (0). Response values are summed, divided by the total number of items responded to (excluding selections of non-applicable items), and multiplied by 13. The raw score is converted using a scoring table to derive both a linear score from 0 (no activation) to 100 (fully activated) and interval patient activation scores (1: activation not important, passive recipient of care; 2: lack of knowledge or confidence to take action; 3: beginning to take action; 4 taking action).

6.4.2. Beliefs about medications

Beliefs about medications is assessed on the baseline and end-of-study surveys, using the 8-item Beliefs About Medicines Questionnaire (BMQ) - General Scale.¹⁴ Each item has five possible response options: (1) *Strongly disagree*, (2) *Disagree*, (3) *Neither agree nor disagree*, (4) *Agree*, (5) *Strongly agree*. A total score reflecting overall beliefs is calculated as a numerical sum across participant responses ranging from 8 to 40. Higher scores represent stronger beliefs about medication overuse and harm. The general use subscale is calculated as a numerical sum using items 1, 3, 4, and 8 ranging from 4 to 20 and represents beliefs about medication overuse. The general harm subscale is calculated as a numerical sum using items 2, 5, 6, and 7 ranging from 4 to 20 and represents beliefs about medication harm. A measure of medication beliefs is derived for each participant at baseline and 6 months after randomization.

6.4.3. Self-reported feelings about genomic testing results

Self-reported feelings about the psychosocial impact of receiving genomic test results will be assessed using the Feelings About genomic Testing Results (FACToR) Questionnaire.²⁵ The FACToR is only administered to the Immediate Results arm.

6.4.4. Preferences for receiving genetic test results

Preferences for receiving genetic test results include two items, developed specifically for this study, to assess 1) preferred first contact for genetic test results (e.g., participant, participant's primary care provider) and 2) preferred provider to deliver results (e.g., research genetic counselor, participant's primary care provider). These items are only administered to the Immediate Results arm.

7.0 Analysis methods

7.1 Covariate adjustment

No prespecified covariate adjustment is planned. If any covariate adjustment is deemed necessary during analysis or used to improve the precision of estimates, rationale and methods will be fully described in the final manuscript(s).

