5.0 Statistical Considerations

5.1 Statistical framework

The principal analysis uses an intention-to-treat (ITT)¹⁵ approach to compare the Immediate Results and Delayed Results arms. Using an independent t-test, analysis of the primary outcome uses a t-statistic, and two-sided type I error rate of 0.05 to test the null hypothesis of no difference in LDL-C change between arms. To quantify the treatment arm difference for the primary endpoint, a mean difference will be presented with a corresponding confidence interval estimate. Mean change in LDL-C is also reported separately for each arm. Similarly, for secondary and other pre-specified outcomes an ITT approach is used to make outcomes comparisons across treatment groups. Subset analyses, including sensitivity and group analyses by demographic, variant confirmation status, or other study or patient characteristics, are considered exploratory and will be described in detail if reported.

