7.2 Primary outcome

The difference in LDL-C reduction after 6 months between the Immediate Results arm and the Delayed Results arm will be assessed. The LDL-C values at baseline and 6 months will first be summarized descriptively for each arm. The change in LDL-C from baseline to 6 months will be calculated for each participant. An independent *t*-test will be employed to compare the mean LDL-C change between the two arms, assuming normally distributed data. If the change scores do not follow a normal distribution, a non-parametric alternative, the Wilcoxon rank-sum test, may be used. The effect size (Cohen's *d*), confidence intervals, and *P* value will be reported to determine the statistical significance of the observed difference. Additionally, potential confounders may be included in regression modeling to ensure the robustness of findings.

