7.4.3 Self-reported quality of life

Mean change scores (6-month scores minus baseline scores) and standard deviations for both PCS and MCS of the VR-12 will be calculated for each arm. Independent samples t-tests will compare differences in mean change between the two arms for both PCS and MCS. Multivariable linear regression models (e.g. ANCOVA) may be fit to account for potential confounding variables.

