7.4.5 Categorical and ordinal outcome measures

The following measures are compared between treatment groups among the ITT populations using standard methods for categorical data analysis:^{27,28}

- Self-reported physical activity
- Self-reported smoking status
- Self-reported saturated fat consumption
- Self-reported patient activation (categorical score)
- Self-reported feelings about genomic testing results (Immediate Results arm only, items)
- Preferences for receiving genetic test results (Immediate Results arm only)

Frequency of end-of-study self-reported responses to study surveys, including categorical, ordinal, and Likert items, will be reported by treatment group (n, %). Binary logistic regression will be used to compare end-of-study dichotomous outcomes between treatment groups. To assess post-treatment ordered outcomes (e.g., lifestyle behaviors along the transtheoretical model continuum) between treatment arms, we will use ordinal logistic regression (e.g., cumulative logit model). Initial models will include treatment group assignment, and when available, baseline measures as covariates.

Treatment effect is characterized by an odds ratio estimate presented with standard error, 95% confidence interval, and *P* value.

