7.4.6 Continuous outcome measures

The following continuous measures are compared between treatment groups among the ITT populations using standard linear methods:^{29,30}

- Self-reported patient activation (linear score)
- Self-reported beliefs about medications
- Self-reported feelings about genomic testing results (Immediate Results arm only, score)

Mean and standard deviation (or median and IQR, if applicable) of continuous scores associated with end-of-study self-reported responses to study surveys will be reported by treatment group. Analysis of covariance (ANCOVA) is used to compare continuous follow-up measures, including participant baseline measures, when available, and treatment group assignment. Treatment effect is characterized by treatment versus control arm, presented as mean follow-up estimates with accompanying standard errors, 95% confidence intervals and *P* values. In the presence of substantial missing data, mixed modeling or other repeated measures designs may be implemented.

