7.5 Additional analyses

Further exploratory analyses using the methods described may be conducted for all study outcomes between treatment arms and across relevant subgroups. Inclusion of additional covariates in the models described or use of alternative statistical methods may be implemented to enhance model precision, to adjust for differences in baseline factors or multilevel characteristics, or to improve the integrity of the analyses (e.g., in the event of substantial missing data), among other reasons. To assess robustness of ITT analyses, analyses may be replicated within the relevant complete case populations. The addition of covariates or use of alternative methods to assess primary, secondary, and other outcomes may be considered and are supplemental to the prespecified analyses.

Additional exploratory analyses may be conducted to further examine study data or address research questions that arise during the conduct of the study. Any exploratory analyses or use of alternative methods will be justified and described in detail if reported.

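### The primary t-test on LDL-C change is valid but gives up precision that adjusting for baseline LDL-C would supply free, and the optional Wilcoxon switch does not test the stated mean difference

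*SAP*

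**What the plan says.** **Primary analysis.** SAP 7.2 computes each participant's change in LDL-C, and an independent t-test "will be employed to compare the mean LDL-C change between the two arms, assuming normally distributed data". Section 5.1 fixes a two-sided type I error of 0.05 and says that "a mean difference will be presented with a corresponding confidence interval estimate".

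**Adjustment.** Section 7.1 opens with "No prespecified covariate adjustment is planned". It then permits adjustment decided during analysis, including for precision, if the rationale is reported. Section 7.2 allows possible confounders in a regression. Under 7.5, added covariates or alternative methods "may be considered and are supplemental to the prespecified analyses".

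**Non-normality.** Within the primary method itself, 7.2 says that if the changes are not normally distributed "a non-parametric alternative, the Wilcoxon rank-sum test, may be used".

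**Other outcomes.** For exploratory continuous scores such as patient activation and medication beliefs, 7.4.6 says ANCOVA "is used to compare continuous follow-up measures, including participant baseline measures, when available, and treatment group assignment". For categorical and ordinal measures, 7.4.5 says: "Initial models will include treatment group assignment, and when available, baseline measures as covariates". Quality of life (VR-12) is treated like the primary outcome: in 7.4.3, t-tests "will compare differences in mean change between the two arms for both PCS and MCS", with ANCOVA only an option.

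**The concern.** There are two linked points.

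The first is efficiency. A change score subtracts the whole baseline value, which amounts to assuming that the slope of follow-up on baseline is 1. ANCOVA estimates that slope. In large samples it is never less precise, and it ties only when the slope really is 1. The SAP uses baseline adjustment for several exploratory outcomes but not for its one confirmatory estimate. Because later covariates are supplemental under 7.5, the precision cannot be recovered in the primary result.

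The second is coherence. Wilcoxon addresses whether values in one arm tend to exceed those in the other, not whether the means differ. If it is substituted, the primary p-value and the reported mean difference with its interval could answer different questions. The SAP states neither what counts as non-normal nor what estimate would accompany the Wilcoxon result.

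**Working it through.** **1. Reproduce the SAP's sample sizes (3.2).** Per arm, n = 2(1.960 + 0.842)² × SD²/δ² (two-sided 0.05, 80% power, 1:1).

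- δ 20, SD 30: 35.3, so 36 per arm and 72 in total.
- δ 20, SD 40, and δ 15, SD 30: 62.8, so 63 per arm and 126 in total.
- δ 15, SD 40: 111.6, so 112 per arm and 224 in total.

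All four rows of the table reproduce. Enrolment of 244 is set by the LDL-C target outcome, which needs 97 evaluable per arm. That 97 is used below.

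**2. Variance of the two estimators.** Let s be the SD of LDL-C, equal at both times, and ρ the baseline to 6-month correlation. The SAP does not give ρ, so it is assumed over 0.3 to 0.9.

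- Change score: 2s²(1 − ρ)
- ANCOVA residual: s²(1 − ρ²)
- Ratio: (1 + ρ)/2 = 0.65, 0.75, 0.85, 0.95 for ρ = 0.3, 0.5, 0.7, 0.9
- Narrowing of the confidence interval: 1 − √ratio = 19.4, 13.4, 7.8, 2.5%

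**3. Power at 97 per arm.** Noncentral t with noncentrality δ/(SD√(2/97)), divided by √ratio for ANCOVA; 192 and 191 degrees of freedom. For example, with δ 15 and SD 40 it is 15/(40 × 0.1436) = 2.61, and at ρ = 0.5 it is 2.61/0.866 = 3.02.

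| Difference, SD (points) | t-test | ANCOVA, ρ 0.3 | ρ 0.5 | ρ 0.7 | ρ 0.9 |
|---|---|---|---|---|---|
| 20, 30 | 99.6% | 100% | 100% | 99.9% | 99.7% |
| 20, 40 | 93.4% | 99.0% | 97.9% | 96.4% | 94.5% |
| 15, 30 | 93.4% | 99.0% | 97.9% | 96.4% | 94.5% |
| 15, 40 | 73.8% | 89.7% | 85.1% | 80.5% | 76.0% |
| 10, 30 (not a SAP row) | 63.7% | 81.7% | 76.0% | 70.7% | 65.9% |

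The last row halves the 20-point effect (20 × 0.5 = 10), using the upper bound in 3.2 of 50% without therapy escalation.

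Simulation of 4,000 trials per setting agreed for the 10-point case: 64% against 81% at ρ 0.3, 63% against 76% at 0.5, and 62% against 69% at 0.7. Under the null, type I error was 4.6–5.2% for the t-test and 4.5–5.1% for ANCOVA.

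**4. Sensitivity of the gain.**

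- *Unequal SDs.* The ratio becomes (1 − ρ²)s₁²/(s₀² + s₁² − 2ρs₀s₁), where s₀ and s₁ are the baseline and 6-month SDs. At ρ 0.5 it is 0.57 if s₁ = 0.8s₀ and 0.87 if s₁ = 1.2s₀, that is, narrowing of 24% or 7%.
- *Baseline carried forward.* Section 6.1 allows this. With a fraction f carried forward and equal SDs, ρ becomes (1 − f)ρ + f. At f = 0.2 and ρ = 0.5 that is 0.8 × 0.5 + 0.2 = 0.6, and narrowing falls from 13.4% to 1 − √0.80 = 10.6%.
- *Scale.* Section 3.2 works in percent change, while 2.2 defines change as end-of-study minus baseline. The variance ratio is exact for absolute change only, so the power figures are indicative.

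**5. The Wilcoxon option.**

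- *Is a switch needed for validity?* With strongly skewed (exponential) changes, t-test type I error was 5.0% at 97 per arm and 5.2% at 72 per arm. It is not needed.
- *Does it test the same thing?* With equal means but different shapes, Wilcoxon rejected in 6.6% of trials and the t-test in 4.6%. When 15% of the Immediate Results arm responds by 60 points (SD 25), Wilcoxon power was 39% against 57%. When 25% responds by 40 points (SD 30), it was 51% against 58%.
- *Worst case.* If the test were chosen by its result, rejecting when either p < 0.05, 40,000 simulated null trials per setting gave type I error of 6.1% for normal changes and 6.7% and 7.5% for shifted lognormal changes (log-SD 0.5 and 0.8). Each test alone gave 4.8–5.1%.

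**The case against.** The t-test is not an error. It is unbiased under randomisation and matches the objective in 2.2 directly. Using ANCOVA for survey scores does not contradict it. Sections 7.1 and 7.5 already allow a baseline-adjusted estimate to be shown beside the primary one. Power exceeds 90% in three of the SAP's four rows, and the size of the gain rests on a correlation that the SAP does not give. All of this stands and limits the point to an improvement. It does not remove it: an adjustment chosen during analysis, or one that is only supplemental, cannot be the primary estimate.

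On Wilcoxon, 7.2 ties the switch to non-normal changes, and 5.6 requires assumptions to be evaluated before analysis and the assessment reported. If the switch followed a fixed normality test, type I error would stay close to 5%. With a Shapiro-Wilk trigger at 0.05, which is an assumption since the SAP names none, simulation gave 5.1% for normal, 4.9–5.1% for lognormal and 5.4% for t-distributed changes with 5 degrees of freedom. The 6.1–7.5% is therefore a bound on misuse, not a consequence of following the plan. What remains is that the wording is permissive, no criterion is given, and the test does not match the mean difference promised in 5.1.

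**Conclusion.** The point holds as a recommended improvement; the primary test and the stated sample sizes are not wrong. Adjusting for baseline LDL-C would narrow the primary confidence interval by about 2.5 to 19% for correlations from 0.9 down to 0.3, assuming equal SDs at the two times. In the SAP's base case this is a precision gain only. It is a material power gain in the 15-point, SD 40% row (74% to 76–90%) or if the effect is diluted to 10 points (64% to 66–82%). The direction is secure; the size depends on the correlation, the SD ratio, the percent-change approximation and the amount of carry-forward. The Wilcoxon wording is a separate gap of coherence, and it holds whatever the correlation.

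**What to change.** Amend three sections of the SAP.

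- **5.1 and 7.2:** make the primary analysis a linear model of 6-month LDL-C on arm and baseline LDL-C in the intention-to-treat population, with robust standard errors. Report the adjusted mean difference, its 95% confidence interval and p-value.
- **7.1:** name baseline LDL-C as the single prespecified covariate for the primary outcome.
- **7.2:** delete the wording that lets Wilcoxon replace the primary test. Keep the unadjusted t-test on change and the Wilcoxon test as sensitivity analyses. Robust standard errors then deal with departures from the usual variance assumptions without changing the quantity estimated.

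The cost is SAP wording only. Baseline LDL-C is already collected for the change score, and no participants are added.

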7.2 Primary outcome

The difference in LDL-C reduction after 6 months between the Immediate Results arm and the Delayed Results arm will be assessed. The LDL-C values at baseline and 6 months will first be summarized descriptively for each arm. The change in LDL-C from baseline to 6 months will be calculated for each participant. An independent *t*-test will be employed to compare the mean LDL-C change between the two arms, assuming normally distributed data. If the change scores do not follow a normal distribution, a non-parametric alternative, the Wilcoxon rank-sum test, may be used. The effect size (Cohen's *d*), confidence intervals, and *P* value will be reported to determine the statistical significance of the observed difference. Additionally, potential confounders may be included in regression modeling to ensure the robustness of findings.

7.3 Secondary outcomes

7.3.1 Proportion meeting LDL-C targets

Proportions of patients meeting individualized cholesterol targets at end of study (yes or no for <100mg/dL for primary prevention and <70 mg/dL for secondary prevention) will be compared between the Immediate Results and Delayed Results arm using either a Z-test of proportions or

chi-squared test. In the event of small cell counts, we will employ Fisher's exact test to ensure the validity of the results. We will compute the relative risk and 95% confidence intervals to quantify the strength and direction of the association. Potential confounders may be adjusted for by using logistic regression. Frequencies and proportions of participants meeting LDL-C targets will be reported by randomization arm.

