3.2 Sample size

The MVP-ROAR-FH Study aims to enroll ten participants into a pilot trial and 244 participants into the RCT.

Sample size is based on the primary outcome of change in LDL-C in each arm after 6 months. Assuming a mean LDL-C reduction of 20% in the Immediate Results arm, a mean LDL-C reduction of 0% in the Delayed Results arm, and a common standard deviation of 30%,² 72 total participants (36 per arm) are needed to have 80% power to detect a significant between-group difference at alpha=0.05. Enrollment of twice this number (144 total) will account for an absence of therapy escalation in up to 50% of participants in the Immediate Results arm. Enrollment of 180 total participants will account for up to 20% loss to follow-up.

| Change in LDL-C at 6 months | | | Total sample size required |
|-----------------------------|-----------------|-----------|----------------------------|
| Immediate Results | Delayed Results | Common SD | |
| -20% | 0% | 30% | 72 |
| -20% | 0% | 40% | 126 |
| -20% | -5% | 30% | 126 |
| -20% | -5% | 40% | 224 |

An important secondary outcome is the proportion of participants in each arm meeting accepted LDL-C targets at 6 months (<100 mg/dL for primary prevention and <70 mg/dL for secondary prevention). In preparatory-to-research analyses, only 175/322 (46%) MVP participants with a potentially pathogenic LDLR variant had a most recent LDL-C <100mg/dL. To have 80% power to detect a between-arm difference of 20% of participants meeting this LDL-C target at alpha=0.05, up to 194 total participants are needed (97 per arm). To account for up to 20% loss to follow-up, a total of 244 participants (122 per arm) are needed.

| Proportion of participants with LDL-C < 100mg/dL at 6 months | | Total sample size required |
|--|-----------------|----------------------------|
| Immediate Results | Delayed Results | |
| 10% | 30% | 124 |
| 20% | 40% | 162 |
| 30% | 50% | 186 |
| 40% | 60% | 194 |

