4.1 Study inclusion and exclusion criteria

Inclusion criteria: A participant is eligible for enrollment in this study if he/she meets the following criteria:

- Is a living enrollee in MVP.
- Is identified to have a pathogenic or likely pathogenic variant in an FH-associated gene in their MVP genotype data.
- Has not previously undergone genetic testing for familial hypercholesterolemia. Study staff first ascertain this by review of the medical record and then confirm during the informed consent call by asking the participants about any prior genetic testing he/she has undergone.
- Is not incarcerated.
- Is not pregnant.

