5.4 Confidence intervals, *P* values, and multiple testing

All statistical testing is reported with an effect, a two-sided 95% confidence interval, and *P* value, unless otherwise specified. *P* values less than 0.05 will be reported as significant for the primary outcome. *P* values reported as significant for secondary outcomes will undergo Bonferroni correction for multiple hypothesis-testing. Other pre-specified and post-hoc analyses are considered exploratory.

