6.2 Secondary outcomes

6.2.1. Proportion meeting LDL-C targets

The proportion of participants meeting individualized clinically significant LDL-C targets (<100mg/dL for primary prevention and <70 mg/dL for secondary prevention) will be determined at 6 months, using the LDL-C values as described for the primary outcome in Section 6.1.

Secondary prevention will be defined as any patient with any of the following:

Pre-existing atherosclerotic disease (ASCVD): acute coronary syndrome in the prior 12 months, history of myocardial infarction, history of ischemic stroke, symptomatic peripheral artery disease including aneurysm, all of atherosclerotic origin.

Presence of any ASCVD risk factors: age ≥ 65 years; prior percutaneous coronary intervention; prior coronary artery bypass graft; other evidence of coronary artery disease; diabetes mellitus; hypertension; chronic kidney disease; current smoking; congestive heart failure; family history of premature ASCVD; elevated coronary artery calcium score, Lp(a), or apoB; or ankle-brachial index < 0.9 .

All other participants will be considered eligible for primary prevention.

The primary or secondary prevention status of each participant will be determined by clinician review of participant medical records through the end-of-study date. The clinician reviewer(s) will be blinded to randomization status. For each participant deemed eligible for secondary prevention, the clinician will record the reason(s) for eligibility in a study database.

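### The LDL-C target outcome that sets N=244 is tested without baseline adjustment: the test is valid, but prespecifying baseline LDL-C as a covariate would recover precision at little cost

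*SAP*

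**What the plan says.** **Outcome.** SAP 6.2.1 defines target attainment as a status that "will be determined at 6 months, using the LDL-C values as described for the primary outcome in Section 6.1". Section 7.3.1 compares "Proportions of patients meeting individualized cholesterol targets at end of study" by a Z-test of proportions or chi-squared test (Fisher's exact test for small cells) and reports a relative risk. It allows logistic regression for confounders that it does not name.

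**Adjustment.** Section 7.1: "No prespecified covariate adjustment is planned". Its next sentence permits adjustment during analysis, including for precision, with the rationale given in the manuscript. Section 7.5 classes added covariates as supplemental to the prespecified analyses.

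**Weight of this outcome.** Section 3.2 states the aim as "To have 80% power to detect a between-arm difference of 20% of participants meeting this LDL-C target at alpha=0.05". The evaluable number it derives is 194, or 97 in each arm, and the enrolment figure follows from it: "To account for up to 20% loss to follow-up, a total of 244 participants (122 per arm) are needed". The primary outcome alone led to 180.

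**Baseline LDL-C.** Section 6.1 defines it, and the primary change score needs it. The entry criterion in 4.1 is genetic ("Is identified to have a pathogenic or likely pathogenic variant in an FH-associated gene in their MVP genotype data"), and no LDL-C level is required.

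**Other outcomes.** For the survey measures, 7.4.5 (logistic and ordinal models) and 7.4.6 (ANCOVA) include the baseline measure whenever there is one.

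**The concern.** The 6-month outcome is a dichotomised LDL-C value, and the same quantity is measured at baseline. Because entry sets no LDL-C level, participants may start anywhere relative to their target, and baseline LDL-C should predict who is below it at 6 months. An unadjusted test leaves that predictable part in the error term.

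The option to adjust later does not recover it. No covariate or model is named, the decision would come after data are available, and 7.5 would not let the result stand as the main analysis. A logistic model would also give an odds ratio, and the SAP has no step linking it to the relative risk that 7.3.1 reports. At stake is the precision of the outcome that determined the trial's size. The plan already takes this precision for outcomes that matter less.

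**Working it through.** **1. Reproduce the plan's figure.** Inputs from 3.2: 40% against 60%, alpha 0.05, power 80%. Tests are two-sided (5.4: "All statistical testing is reported with an effect, a two-sided 95% confidence interval"). Pooled-variance formula per arm:

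n = [1.96·√(2·0.5·0.5) + 0.8416·√(0.4·0.6 + 0.6·0.4)]² / 0.20² = (1.386 + 0.583)² / 0.04 = 96.9, so 97 per arm and 194 in total.

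For 20% loss: 97/0.8 = 121.25, so 122 per arm and 244. Both figures reproduce for the unadjusted test. They take no credit for baseline.

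**2. Gain from adjustment.** The SAP gives no correlation ρ between baseline and 6-month LDL-C, so ρ is assumed and a range is shown. Baseline and 6-month LDL-C were simulated as bivariate normal and the 6-month value was cut to give 40% and 60% at target, with 97 per arm and 3,000 trials per setting. The unadjusted Z-test was compared with a logistic model on arm and continuous baseline. The raw risk difference was compared with the standardised one.

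| ρ (assumed) | Variance ratio, adjusted/raw | Power, raw | Power, adjusted | Equivalent N (194 × ratio) |
|---|---|---|---|---|
| 0.3 | 0.943 | 81% | 83% | 183 |
| 0.5 | 0.831 | 82% | 88% | 161 |
| 0.7 | 0.666 | 80% | 93% | 129 |

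Monte Carlo error on power near 80% is √(0.8·0.2/3000) = 0.7 points, which accounts for the spread in the raw column. Repeat runs gave ratios of 0.94 to 0.96 at ρ = 0.3, 0.83 at 0.5 and 0.69 to 0.70 at 0.7. Adjusted power in those runs was 82%, 87% to 88% and 93% to 94%. The mean risk difference stayed at about 0.20 with and without adjustment.

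**3. Hand check.** The raw standard error is √(0.48/97) = 0.0703. With the ratio 0.831 it becomes 0.0703·√0.831 = 0.0641. Power is then Φ(0.20/0.0641 − 1.96) = Φ(1.16) = 88%, as simulated.

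**4. Sensitivity.**
- Adjusting only for at target at baseline, yes or no, gives ratios of 0.96, 0.90 and 0.80 at ρ = 0.3, 0.5 and 0.7. The continuous value is better.
- At 10% against 30% (62 per arm) the ratios are 0.88 (ρ = 0.5) and 0.76 (ρ = 0.7), so the gain does not need about half of participants to be at target.
- Type I error of the adjusted analysis was 4.5% to 5.9% at nominal 5%.
- Section 5.4 applies Bonferroni to the secondary outcomes, and 6.2 lists two. At 0.05/2 = 0.025, raw power with 97 per arm is about 71%; adjustment at ρ = 0.5 brings it to about 79%.

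**The case against.** The strongest reply is that nothing here is an error. Randomization makes the raw comparison unbiased, the 95% interval already covers chance imbalance at baseline, and 244 is right for the named test. That stands. It also stands that 7.1 and 7.5 mention adjustment for precision, though only after the fact and as a supplement. Further, 97 per arm is the full-attrition case. Section 6.1 allows record values and carry-forward, so the analysed number may approach 122 per arm, where raw power is about 88% (82% at alpha 0.025). The extra power from adjustment would then matter less.

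The documents do not support three stronger readings that a reader might infer:

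- **That most of the variation in the outcome is baseline standing.** In the latent-normal model, continuous baseline LDL-C explains about 10%, 16%, 23% and 32% of the within-arm outcome variance at ρ = 0.4, 0.5, 0.6 and 0.7.
- **That roughly half of participants are already at target.** The figure in 3.2 is for LDL-C <100 mg/dL in carriers of an LDLR variant. The outcome uses <70 mg/dL for secondary prevention, which 6.2.1 defines broadly. The share at the individualized target is not given, and in the same people it cannot exceed the <100 mg/dL share. The printed count and percentage also disagree: 175/322 = 54%, while 46% would correspond to 147/322. They need reconciling.
- **That adjustment changes who counts as a success.** A participant below target throughout is still counted. The proportion at target at 6 months is a legitimate quantity, and only its precision changes.

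**Conclusion.** The point holds as an avoidable loss of precision and a gap in prespecification. It is not a fault of validity or of the sample size. With 97 per arm and 40% against 60%, naming continuous baseline LDL-C as a covariate cuts the variance of the risk difference by about 5% to 30%, and power goes from about 80% to about 82% to 94%. This rests on an assumed correlation of 0.3 to 0.7 and a normal latent model; at the low end the gain is slight. The case for the change comes less from any single value in that range than from its low cost and from the SAP's own practice in 7.4.5 and 7.4.6.

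**What to change.** In 7.3.1, prespecify as the main analysis a logistic model with arm and continuous baseline LDL-C (the 6.1 value). Standardise it over the whole ITT sample to an adjusted risk difference and relative risk, with robust or bootstrap 95% intervals. Keep the raw proportions by arm and the chi-squared test as supportive. Amend 7.1 to match.

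Add a rule that keeps in the analysis participants whose baseline LDL-C is missing or was taken after randomization (4.3.1 foresees the latter). One example is single imputation of the baseline value without regard to arm. Since 5.5 has imputation done separately within each arm, mark this as an exception for the baseline covariate.

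The cost is SAP wording and a few lines of code, with no new data. The downside is that a standardised estimate takes slightly more explaining than raw proportions, which are still shown.
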